10.2 Protocol Deviations

Summary statistics of the frequency and percentage of patients in the SAS with critical PDs for each deviation category will be provided by cohort and overall. A patient with multiple occurrences of a critical PD in the same deviation category will only be counted once in that category. A listing of PDs by cohort will be provided for all patients in the SAS, along with the classification of deviation.

10.3 Demographics and Baseline Characteristics

The list below presents the list of demographic and baseline characteristic variables that will be summarized by cohort and overall, for patients in the SAS; and repeated for the EDFS1, if unique to support the primary endpoint.

- Age (years). Age will be used as calculated in the database.
- Sex (Female, Male, Unknown, Not Reported)

- Childbearing potential (Yes, No)
- Ethnicity (Hispanic or Latino, Not Hispanic or Latino, Unknown, Not reported)
- Race (American Indian or Alaska Native, Asian, Black or African American, Native Hawaiian or Other Pacific Islander, White, Not Reported, Unknown, Multiracial, Not reported, Other)
- Height (cm) at screening
- Weight (kg) at screening
- BMI (kg/m²) at screening. BMI will be derived by using the following formula:
$$BMI = Weight (kg) / [Height (m)]^2$$
- ECOG performance status at baseline (0, 1, 2, 3, 4, 5)

For continuous parameters, mean, standard deviation, Q1, median, Q3, minimum, and maximum will be displayed. Categorical data will be presented using numbers and percentages. The denominators for percentages will be the number of patients in each cohort and overall, with non-missing data for the variable of interest. A listing for patient's demographics and baseline characteristics based on the SAS will also be produced.

10.3.1 Medical and Surgical History

Medical history, including surgical history, will be coded using MedDRA Version 25.0. A summary table by SOC and PT, along with a corresponding by patient listing of medical history (including SOC and PT), will be presented for the SAS.

No imputation of partial or missing dates will be performed for medical history and study days will not be presented for these cases.

10.4 Prior and Concomitant Medications and Procedures

Prior and concomitant medications will be coded using Version B3, Mar 2022 of the WHO drug dictionary. All medications started and ended prior to the first administration of study drug will be considered prior medications. All medications started prior to the first study drug administration and ongoing at the time of administration, or taken from the time of first study drug administration to the end of follow-up will be considered concomitant medications.

Partial and missing dates for medications will be imputed using the guidance in [Table 7](#). The recorded partial/missing dates will be displayed in the listings and study days will not be presented for these cases.

Prior and concomitant medications will be listed for the SAS by WHO ATC level 3, preferred term, and cohort.

Concomitant non-pharmacologic treatments/procedures will be coded using MedDRA Version 25.0 and will be listed per patient for the SAS. The listing includes procedure number, SOC, PT, procedure name, primary reason for treatment/procedure, medical history number, AE number, indication, treatment/procedure date, and concomitant medication number (if applicable).

10.5 Study Drug [⁶⁸Ga]FAPI-46 Administration and PET Scan

The proportion and percentage of patients receiving each dose, along with descriptive statistics summarizing the dose amount and corresponding image quality of the PET scan, will be summarized by cohort for the SAS.

A listing displaying each dose (single dose in Cohort 1 and 2 doses in Cohort 2) of [⁶⁸Ga]FAPI-46, including the date and time of study drug administration, dose (mCi), date of image, imaging start time, and image quality will be provided using the SAS.

10.6 Efficacy

Efficacy analysis will be presented overall, ie, both cohorts combined. For the primary analysis, a single readable [⁶⁸Ga]FAPI-46 PET image result will be compared with a corresponding histopathology result. For patients in Cohort 2 with multiple PET scans, the most recent PET scan performed prior to surgery will take precedence for analysis.

10.6.1 Testing Statistical Assumptions Including Comparability at Baseline

10.6.1.1 Test of Proportions

The assumption underlying the normal approximation to the binomial distribution, used in the computation of CIs for sensitivity is that the sample size is such that $np > 5$ and $n(1-p) > 5$, where n is the sample size and p is the binomial probability. It is expected that the sample size for each statistic will be sufficient to meet this assumption. In the event that the sample size is not sufficient, Agresti-Coull exact tests will be used. As there is only 1 treatment in this study, there will be no testing of baseline comparability.

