6.1.2 Justification of Sample Size

The sample size is 60 patients in order to adequately power the primary objective of sensitivity.

For this study, the primary efficacy endpoints is sensitivity, evaluated with a hypothesis test:

H0: Sensitivity \leq PG

H1: Sensitivity $>$ PG

The minimum sample size necessary to achieve power for sensitivity was computed for the hypothesis test above utilizing a one-sample binomial proportion test with a normal approximation, an upper one-sided significance level of 0.05, and the following parametric assumptions:

- PG = 0.75 for sensitivity
- True Sensitivity = 0.90

Given the parametric assumptions above, 60 patients yields 92.7% power to demonstrate that the true sensitivity is greater than 0.75.

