10.6.2 Primary Analysis

The primary analysis will evaluate the performance (measured by sensitivity) of [⁶⁸Ga]FAPI-46 PET imaging to detect PDAC, using histopathology as truth standard.

The primary efficacy endpoints will compare positive/negative status from [⁶⁸Ga]FAPI-46 PET and histopathology of the primary lesion and the analysis will be based on the EFS1, as defined in [Section 7.1.2.1](#).

The table below contains terms used to define sensitivity.

Table 4. ⁶⁸Ga]FAPI-46 PET vs Histopathology

		Histopathology		
		Positive	Negative	
⁶⁸ Ga]FAPI-46 PET	Positive	A	B	A + B
	Negative	C	D	C + D
Total		A + C	B + D	N

A = true positive; B = false positive; C = false negative; D = true negative; FAPI = fibroblast-activation-protein inhibitors; PET = positron emission tomography
 N indicates the number of patients with FAPI-46 and corresponding histopathology results.

The sensitivity, which evaluates how good a test is at detecting a positive disease, will be calculated as:

$$\text{Sensitivity} = A / (A + C)$$

The point estimate, SE, as well as the 90% asymptotic normal CI will be presented for sensitivity. The 95% asymptotic normal CI will also be presented; however, the primary focus will be on the 90% CI to align with the 5% one-sided test.

Inference for the primary hypotheses will be conducted utilizing a one-sample binomial proportion test with a normal approximation given the assumptions have been met (see [Section 10.6.1.1](#)), a one-sided upper significance level of 0.05, and assumed null proportions/PGs of 0.75 for sensitivity. Success for the primary efficacy analysis will be defined as demonstrating that the sensitivity is statistically significantly greater than its PG. The one-sided asymptotic p-value will be provided for sensitivity. Refer to [REDACTED]

A listing of ⁶⁸Ga]FAPI-46 PET imaging results, including histopathology disease presence associated with the corresponding region (same lesion) will be presented for the SAS with a record identifier for patients in the EDFS1.

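### The headline 90% Wald interval does not match the primary sensitivity test, and the named small-sample fallback is not a defined procedure; one exact test with its own interval settles both

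*SAP*

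**What the plan says.** SAP 6.1.2 sets the planning values: "PG = 0.75 for sensitivity", "True Sensitivity = 0.90", "an upper one-sided significance level of 0.05", and the result that "60 patients yields 92.7% power to demonstrate that the true sensitivity is greater than 0.75".

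SAP 10.6.2 bases inference on a "one-sample binomial proportion test with a normal approximation given the assumptions have been met". Success is statistical significance against the performance goal, with a one-sided asymptotic p-value. The reported interval is the asymptotic normal one at 90% and at 95%. The SAP says that "the primary focus will be on the 90% CI to align with the 5% one-sided test"; the estimand table (5.2) and the table of changes from the protocol (Section 8) give the same reason.

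SAP 10.6.1.1 makes the normal approximation conditional on np > 5 and n(1-p) > 5. It adds: "It is expected that the sample size for each statistic will be sufficient to meet this assumption". Failing that: "In the event that the sample size is not sufficient, Agresti-Coull exact tests will be used".

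The readable text does not name the variance used in the test, the p that enters the check, or an interval to go with the fallback.

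**The concern.** Sensitivity is the only primary hypothesis, so its test, its interval and any fallback should each be runnable in one way only, and should agree. Two things prevent that.

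- **Interval and test.** An asymptotic normal (Wald) interval takes its standard error from the observed proportion. A z-test against a performance goal normally takes its standard error from the goal. The two need not agree near the cut-off, although the SAP presents them as aligned.
- **Fallback.** Agresti-Coull is an adjusted approximate confidence interval. It is not exact, it is not a test, and it supplies no p-value. A programmer would have to choose between an exact binomial p-value and an approximate interval, and would first have to decide which p triggers the choice.

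At stake is a report in which the headline interval and the p-value point different ways, or in which the method is settled after the result is known.

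**Working it through.** **Inputs** (SAP 6.1.2 and 10.6.2): n = 60, p0 = 0.75, p1 = 0.90, one-sided alpha 0.05, z = 1.645.

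**1. Reproducing the stated power.** The null standard error is √(0.75 × 0.25/60) = 0.0559. The z-test rejects when X/60 > 0.75 + 1.645 × 0.0559 = 0.842, that is X > 50.5, so X ≥ 51.

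- Binomial count: P(X ≥ 51 | 0.90) = 0.927, the stated 92.7%. True size: P(X ≥ 51 | 0.75) = 0.0452.
- Normal formula: Φ[(0.15 − 1.645 × 0.0559)/√(0.90 × 0.10/60)] = 93.3%.
- With the sample variance instead, the cut-off is 50. Power is then 96.6% by binomial count (98.7% by formula), and size is P(X ≥ 50 | 0.75) = 0.0859.
- With a continuity correction, power is 85.8% by count (90.0% by formula).

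Only the null-variance z-test, or the exact test that shares its cut-off, gives 92.7%.

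**2. Test against interval at n = 60.** At 50/60 the estimate is 0.8333.

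- z-test: (0.8333 − 0.75)/0.0559 = 1.491, p = 0.068. Not significant.
- 90% Wald: SE = √(0.8333 × 0.1667/60) = 0.0481; limits 0.8333 ± 1.645 × 0.0481 = 0.754 to 0.912. Excludes 0.75.

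At 51/60 both pass (z = 1.789, p = 0.037). So X = 50 is the only discordant count, with probability 0.0859 − 0.0452 = 4.1% at a true sensitivity of 0.75 and 3.9% at 0.90.

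**3. When the fallback triggers at n = 60.**

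- p = null value: 60 × 0.25 = 15. Never triggers.
- p = planning value: 60 × 0.10 = 6. Does not trigger, but would at n ≤ 50.
- p = observed value: triggers with 5 or fewer misses. The probability is 43.7% if true sensitivity is 0.90.

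**4. Whether the switch could alter success.** At 55/60 the z-test p is 0.0014, the exact p is 0.0010 and the 90% Agresti-Coull lower limit is 0.836. All succeed, and fewer misses only strengthens the result. For every n from 40 to 60, n − 5 detections succeed under the z-test, the exact test and the Agresti-Coull limit.

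**5. The exact alternative at n = 60.** The exact one-sided p is 0.0452 at 51 and 0.0859 at 50, so the cut-off is again 51, with size 4.5% and power 92.7%. The 90% Clopper-Pearson lower limit is 0.753 at 51 and 0.734 at 50, so it agrees with the test at both counts.

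**6. Evaluable numbers below 60.** Enrolment is up to 60, uninterpretable scans are excluded (SAP 7.1.2), and replacement is at the sponsor's discretion (protocol 6.1, 6.4.4). The tests coincide at n = 50–52, 55–57 and 60. They differ here (power at 0.90):

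| n | z-test cut-off, size, power | Exact cut-off, size, power |
|---|---|---|
| 53 | 45, 6.1%, 92.2% | 46, 2.8%, 84.4% |
| 54 | 46, 5.3%, 91.4% | 47, 2.4%, 83.2% |
| 58 | 49, 6.0%, 94.0% | 50, 2.9%, 87.9% |
| 59 | 50, 5.2%, 93.3% | 51, 2.5%, 86.9% |

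**The case against.** The best defence is that alignment may mean no more than matching 5% in one tail, which a 90% two-sided level does and a 95% level does not. On that reading the SAP never promised that interval and test would always agree. The disagreement is also confined to one count in 60, and at n = 53, 54 and 58 the Wald and z-test cut-offs coincide.

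The variance form is inferred from the power figure. SAP 10.6.2 has a redacted cross-reference just after the p-value sentence, so computational detail may sit there, and silence on the variance should not be held against the plan.

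Finally, at n = 53, 54, 58 and 59 the z-test exceeds 5% by at most 1.1 points, while the exact test falls to 2.4–2.9%. Preferring the exact test in a single-arm Phase 2 study is partly a matter of taste.

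Much of this stands: it limits the size of the problem and leaves room for a milder remedy. It does not rescue the text. The variance question does not matter to the conclusion: with the null variance the interval and test can conflict, and with the sample variance they agree but size is 8.6% and power is 96.6%, not 92.7%. Neither choice gives a 5% test, the stated power and a matching Wald interval together. The fallback wording has no reading on which it names a real procedure.

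**Conclusion.** The point holds as an error in the text of the primary inference that should be fixed. It does not overturn the design. At n = 60 the interval and the test conflict at 50/60, an outcome with probability about 4% at either planning value, assuming the null-variance z-test that the stated power implies. The fallback is undefined, and so is its trigger; if the observed proportion is meant, it would be invoked 44% of the time at a true sensitivity of 0.90.

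A reader might infer three stronger conclusions, which the documents do not support.

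- **That the trial's type I error is 8.6%.** That is the error of judging success by the Wald limit (or of a sample-variance test). SAP 10.6.2 defines success by the test, and SAP 9.2 ties error control to rejecting the null hypothesis. With the null variance, true size at n = 60 is 4.5%.
- **That the data-driven switch could change the trial's conclusion.** It cannot: on the observed-value reading it operates only where every candidate method already succeeds.
- **That perfect detection would yield a zero-width headline interval.** At 60/60 the Wald interval is indeed 1.000 to 1.000, but that result would also fail an observed-value check. The interval would be reported only if the check uses another p or the fallback is taken to replace the test alone.

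The harm is therefore a contradictory or undefined headline interval. Separately, the z-test's true size is 5.2–6.1% at n = 53, 54, 58 and 59.

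**What to change.** Before the primary analysis is run, delete the np and n(1-p) condition and the Agresti-Coull sentence from SAP 10.6.1.1. In 10.6.2, 5.2 and Section 8, specify one method for all n: a one-sided exact binomial test of sensitivity against 0.75 at 0.05, with the two-sided 90% Clopper-Pearson interval as the primary interval and the 95% version as descriptive. Both changes are needed, because an exact test beside a Wald interval would still conflict at 50/60.

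The cost is a short SAP amendment and one program. No power is lost at n = 60, 50–52 or 55–57. At n = 53, 54, 58 and 59 power falls by 6 to 8 points, because the error above 5% is removed.

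If the sponsor prefers to keep the z-test, the minimum correction is to state that it uses the null variance, report the 90% Wilson score interval, which inverts that test, and delete the fallback sentence. That keeps the z-test's power, but also its true size above 5% at those four sample sizes.

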10.6.2 Primary Analysis

The primary analysis will evaluate the performance (measured by sensitivity) of [⁶⁸Ga]FAPI-46 PET imaging to detect PDAC, using histopathology as truth standard.

The primary efficacy endpoints will compare positive/negative status from [⁶⁸Ga]FAPI-46 PET and histopathology of the primary lesion and the analysis will be based on the EFS1, as defined in [Section 7.1.2.1](#).

The table below contains terms used to define sensitivity.

Table 4. ⁶⁸Ga]FAPI-46 PET vs Histopathology

		Histopathology		
		Positive	Negative	
⁶⁸ Ga]FAPI-46 PET	Positive	A	B	A + B
	Negative	C	D	C + D
Total		A + C	B + D	N

A = true positive; B = false positive; C = false negative; D = true negative; FAPI = fibroblast-activation-protein inhibitors; PET = positron emission tomography
 N indicates the number of patients with FAPI-46 and corresponding histopathology results.

The sensitivity, which evaluates how good a test is at detecting a positive disease, will be calculated as:

$$\text{Sensitivity} = A / (A + C)$$

The point estimate, SE, as well as the 90% asymptotic normal CI will be presented for sensitivity. The 95% asymptotic normal CI will also be presented; however, the primary focus will be on the 90% CI to align with the 5% one-sided test.

Inference for the primary hypotheses will be conducted utilizing a one-sample binomial proportion test with a normal approximation given the assumptions have been met (see [Section 10.6.1.1](#)), a one-sided upper significance level of 0.05, and assumed null proportions/PGs of 0.75 for sensitivity. Success for the primary efficacy analysis will be defined as demonstrating that the sensitivity is statistically significantly greater than its PG. The one-sided asymptotic p-value will be provided for sensitivity. Refer to [REDACTED]

A listing of ⁶⁸Ga]FAPI-46 PET imaging results, including histopathology disease presence associated with the corresponding region (same lesion) will be presented for the SAS with a record identifier for patients in the EDFS1.

10.6.3 Secondary Analysis

The secondary analysis will determine the correlation between ⁶⁸Ga]FAPI-46 PET imaging and IHC, using SUV_{max} and H-score respectively.

The analysis will be based on the EDFS2, as defined in [Section 7.1.2.2](#). The correlation between SUV_{max} and H-score will be analyzed by Spearman's rho test. The correlation coefficient and 95% CI will be provided. Spearman's rho test assesses how well the relationship between 2 variables (ordinal or continuous) can be described using monotonic functions. As it is not evident that the relationship between SUV_{max} and H-score will be linear, Spearman's rho test has been selected instead of Pearson's correlation. The correlation between SUV_{mean} and H-score will also be analysed in a similar manner to SUV_{max}.

The correlation between SUV_{max} vs H-score will be plotted graphically by using a scatterplot.

Sensitivity and specificity will be calculated and presented in the same manner as described for the primary analysis, using IHC as the truth standard. This analysis is for exploratory purposes only.

The specificity, which estimates how likely patients without the disease can be correctly ruled out, will be calculated as:

$$\text{Specificity} = D / (B + D)$$

10.6.4 Other Secondary Analyses

Refer to [Section 10.7](#) for the safety analysis (third secondary endpoint).

10.6.5 Exploratory Analyses

All exploratory analyses will be conducted on the efficacy population defined for each analysis, and will be summarized by cohort, visit, and, where applicable, by region. The data for these presentations will be obtained from the following eCRFs (and associated imaging results):

- Non – Target/Non-Index Lesions
- Target/Index Lesions

10.6.5.1 PET Intensity

Descriptive analyses will be performed on PET intensity parameters and the following summaries will be produced:

- SUV_{max}, SUV_{mean}, and TBR in identified lesions using PET scan (EFFF1).
- SUV_{max}, SUV_{mean}, and TBR in identified lesions using PET scan and correlated with conventional [¹⁸F]-FDG PET scan for the same lesion if data is available. The correlation between [⁶⁸Ga]FAPI-46 PET and [¹⁸F]-FDG PET scan will be analyzed by Pearson's correlation test. The correlation coefficient and 95% CI will be provided (EFFF3).
- SUV_{max}, SUV_{mean}, and TBR differences between pre-NAT and post-NAT in the primary lesion for Cohort 2 using PET scan (EFFF4).

10.6.5.2 Tumor Lesions Detected by [⁶⁸Ga]FAPI-46 PET in Comparison with CT/MRI and/or [¹⁸F]-FDG PET

In addition to the primary lesion, a maximum of 3 LN was assessed by the reader. The number of identified LN detected by [⁶⁸Ga]FAPI-46 PET scan versus the standard of care assessments CT/MRI and/or [¹⁸F]-FDG PET, will be presented for the EFFF3 by cohort and visit, including pre-NAT and post-NAT differences for Cohort 2.

10.6.6 Other Exploratory Analysis

No other exploratory analyses are planned for this study.

10.6.7 Interim Analysis

No formal interim analysis is planned for this study.

10.7 Safety and Tolerability

All safety analyses will be based on the SAS.

Safety variables will be summarized by cohort (including overall) and visit where applicable.

10.7.1 Adverse Events

The verbatim terms used in the eCRF to identify AEs will be coded using MedDRA Version 25.0. AE severity will be evaluated utilizing the CTCAE Version 5.0 ([Appendices](#)) toxicity grade as Grade 1, Grade 2, Grade 3, Grade 4, or Grade 5.

For the purposes of this study, the AE collection window is from the time of injection with [⁶⁸Ga]FAPI-46 through 24 hours postinjection. If the 24-hour window ends on a holiday or nonclinic day (or the patient cannot return to clinic due to unforeseen circumstances, such as weather), the window may be extended until 72 hours postinjection. TEAE summaries will present all AE recorded in the eCRF.

AE collection windows are tied to the number of [⁶⁸Ga]FAPI-46 injections. Cohort 1 will have 1 AE collection window whereas Cohort 2 will have 2 discrete AE collection windows. All collected AEs will be considered TEAE.

A TEAE overview table containing the frequency and percentage of patients as well as number of reported events in each of the following categories (summarized by cohort) will be presented:

- TEAEs
- Serious TEAEs
- TEAE by maximum toxicity grade (CTCAE Version 5.0)
- Study drug-related TEAEs
- Serious study drug-related TEAEs
- Fatal TEAEs

Additionally, the following will be summarized by cohort, SOC, and PT:

- TEAEs
- Serious TEAEs

- TEAEs by maximum toxicity grade (CTCAE Version 5.0)
- Study drug-related TEAEs
- Fatal TEAEs

Summaries of TEAEs by SOC and PT will be sorted alphabetically by SOC and by decreasing frequency of PT overall. If a patient has more than 1 TEAE at a given level (eg, SOC and/or PT), the patient will only be counted once within that level. When summarizing TEAEs by maximum CTCAE toxicity grade, at each level of summarization, patients who report 1 or more TEAEs within that level are only counted once at that level using the event of greatest CTCAE toxicity grade (in toxicity tables). Patients who have reported TEAEs that are missing CTCAE toxicity grade or relationship to study drug will not be summarized in the tables by toxicity grade or relatedness, however they will be included in the listings of AEs and tables not summarized by toxicity grade or relatedness. All tables will show the number and percent of patients with at least 1 TEAE (or SAE, per the criteria in the table).

The following listings will be provided:

- Listing of all TEAEs.
- Listing of patients with serious TEAEs
- Listing of patients with TEAEs leading to Death

Refer to Section 7.2 in the protocol Version 5.0, 31 Mar 2023, for AE definitions applicable to this study. This includes definitions for: life-threatening AEs or life-threatening suspected adverse reaction, suspected adverse reaction, routine AEs, serious AEs or serious suspected adverse reaction, unexpected AEs or unexpected suspected adverse reaction, severity grading, AEs leading to study discontinuation, attribution to investigation medical product and study procedures.

The data for these presentations will be obtained from the Adverse Events and Adverse Events Details eCRF.

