5.2.4. Safety endpoints

- Incidence and severity of TEAEs or TSEAEs 24 hours from [^{68}Ga]FAPI-46 administration according to MedDRA/CTCAE V.5.0.

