5.2 Estimands

The estimand approach for the primary and secondary endpoints is presented in [Table 2](#).

Table 2. Endpoints and Estimands

Endpoint	Estimand
Primary	
Per patient Sensitivity to detect PDAC using histopathology as truth standard.	
a) Population: EFFS1
 
b) Endpoint: Positive/Negative status according to ⁶⁸Ga]FAPI-46 PET and Positive/Negative status according to histopathology (See Table 10) for the primary lesion
 
c) Intercurrent event(s): There are no intercurrent events prespecified.
 
d) Population level summary measure^a:
 
 Sensitivity: point estimate, SE, 90% asymptotic normal CI and p-value
Secondary	
H-score correlated to the uptake of ⁶⁸ Ga]FAPI-46, using SUV _{max} .	
a) Population: EFFS2
 
b) Endpoint: SUV_{max} and H-score^b
 
c) Intercurrent event(s): There are no intercurrent events prespecified.
 
d) Population level summary measure: Spearman correlation coefficient and 95% CI

Incidence and severity of TEAEs or TESAEs	
Note: In addition, sensitivity and specificity of ⁶⁸Ga]FAPI-46 PET to detect FAP-expressing cells using H-score as standard of truth will be presented.
 
a) Population: SAS
 
b) Endpoint: Incidence of AEs
 
c) Intercurrent event(s): There are no intercurrent events prespecified.
 
d) Population level summary measure: Frequency and percentages of patients with each type of TEAE in each cohort.
 
 TEAEs Serious TEAEs TEAEs by maximum severity Study drug-related TEAEs Fatal TEAEs

Abbreviations: AE = adverse event; CI = confidence interval; CT = computed tomography; Efficacy analysis set; FAP = fibroblast activation protein; FAPI = fibroblast-activation-protein inhibitors; FDG = fluorodeoxyglucose; IHC = immunohistochemistry; NPV = negative predictive value; PDAC = pancreatic ductal adenocarcinoma; PET = positron emission tomography; PPV = positive predictive value; SAS = Safety analysis set; SE = standard error; SUV = standardized uptake value; SUV_{max} = maximum standardized uptake value; TEAE = treatment emergent adverse event; TESAE = treatment emergent serious adverse event

- a The primary focus will be on the 90% confidence interval CI to align with the 5% one-sided test; however, the 95% asymptotic normal confidence interval will also be presented for descriptive purposes.
- b SUV_{mean} will also be compared to IHC H-score for exploratory purposes.

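### Adverse events are collected per injection, but the planned TEAE tables are per patient only, so Cohort 2 and overall percentages carry unequal exposure and no TEAE summary by injection is specified

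*SAP*

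**What the plan says.** **Collection.** Protocol 5.2.4 anchors the safety endpoint in time to an administration: "Incidence and severity of TEAEs or TSEAEs 24 hours from" dosing. Protocol 7.2.1 and SAP 10.7.1 open a window at injection and close it at 24 hours, with a proviso that "the window may be extended until 72 hours postinjection". SAP 10.7.1 states that "AE collection windows are tied to the number of" injections, and then: "Cohort 1 will have 1 AE collection window whereas Cohort 2 will have 2 discrete AE collection windows". Protocol 7.2.1 also asks for any event suspected to be related to the tracer, whether or not it falls inside a window.

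**Analysis.** The safety estimand in SAP 5.2, Table 2 is "Frequency and percentages of patients with each type of TEAE in each cohort". In SAP 10.7.1 the overview table gives "frequency and percentage of patients as well as number of reported events", by cohort, and the detailed tables are by cohort, SOC and PT. If a patient has several events at a level, "the patient will only be counted once within that level", and "All tables will show the number and percent of patients with at least 1 TEAE". Every collected AE is treated as a TEAE. Protocol 8.2 sets the denominator as patients who had at least one dose.

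**Nearby text.** SAP 10.7 says safety variables are summarised by cohort, overall and, where it applies, by visit. SAP 10.7.2 and 10.7.3 do this for laboratory results and vital signs. SAP 10.5 tabulates the patients receiving each dose.

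**The concern.** A Cohort 2 patient who has both scans has two windows in which to be counted; a Cohort 1 patient has one. The two percentages nonetheless appear in parallel columns and are pooled in an overall column. A higher Cohort 2 figure could be read as poorer tolerability when it reflects only the number of injections. The overall figure depends on the cohort mix, which the documents do not fix.

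The Cohort 2 column is not a clean two-injection rate either. Protocol 6.1 and 6.4.1 foresee Cohort 2 patients who never have the second scan, and SAP 7.1.1 keeps anyone who received any amount of tracer in the safety set.

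At stake is the reading of a secondary objective, the further characterisation of safety. No hypothesis test is involved.

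**Working it through.** **The plan's own figure.** None is stated for safety. The one computed design figure, 92.7% power for sensitivity, reproduces: rejecting at 51 or more of 60 gives exact power 0.9269 and exact one-sided alpha 0.0452. It plays no part in what follows.

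**Inputs.** Windows per patient are 1 in Cohort 1 and up to 2 in Cohort 2 (SAP 10.7.1). The counting unit is the patient (SAP 5.2, SAP 10.7.1, Protocol 8.2). The per-injection risk p and the share s of patients dosed twice are not in the documents, so both are assumed and shown as ranges. I take p to be equal at both injections and within-patient dependence to be zero or positive.

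**Step 1: patients dosed twice.**
- Same patients react each time: per-patient risk = p (ratio 1).
- Independent events: per-patient risk = 1-(1-p)^2 = 2p - p^2 (ratio 2 - p).

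| p | Lower end | Upper end | Ratio at upper end |
|---|---|---|---|
| 2% | 2% | 1 - 0.98^2 = 3.96% | 1.98 |
| 5% | 5% | 1 - 0.95^2 = 9.75% | 1.95 |
| 10% | 10% | 1 - 0.90^2 = 19.0% | 1.90 |
| 20% | 20% | 1 - 0.80^2 = 36.0% | 1.80 |

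**Step 2: incomplete second dosing.** If only 70% of Cohort 2 (assumed) receive the second injection, p = 10% under independence gives 0.3 x 10% + 0.7 x 19% = 16.3%, not 19.0%.

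**Step 3: overall column, under independence.** Risk = (1-s)p + s[1-(1-p)^2].

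| p | s = 25% | s = 50% | s = 75% |
|---|---|---|---|
| 5% | 6.2% | 7.4% | 8.6% |
| 10% | 12.3% | 14.5% | 16.8% |

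The same tracer risk thus yields different overall figures according to the mix alone.

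**Step 4: assigning events to an injection.** SAP Appendix 2, Table 6 refers partial AE start dates to the first dose only. Suppose a Cohort 2 event follows the second injection, only its year is known, and that year is the year of the first dose. It is imputed to the first-dose date and would move to the wrong injection. If only the day is missing and the month is later than that of the first dose, the imputed date is the first of the month, which may precede the second injection.

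**The case against.** The strongest reply is that nothing is inconsistent. Tying a window to an injection governs when events are collected, not the unit of analysis. Protocol 8.2 and the SAP estimand both use patients, which is conventional, and neither calls the result a per-injection rate. This stands: a reader might infer that the SAP analyses a different endpoint from the protocol's, and the documents do not support that.

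A reader might also infer that the second injection is never shown. That goes too far. Laboratory results and vital signs are presented by visit or time point, SAP 9.3 defines a post-NAT baseline before the second dose, all TEAEs are listed, and SAP 10.1 and 10.5 list the dose dates. With about 60 patients, events can be matched to injections by hand. Event counts and doses by cohort would also give crude events per injection. What remains is that reconstruction from listings is not a prespecified summary, the event counts are not split by injection, and the general rule in SAP 10.7 leaves open whether AEs are among the by-visit tables.

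Third, the size may be slight. No comparison of cohorts on safety is planned and the tables are descriptive. Protocol 4.4 reports more than 200 scans without a reported AE. That is a personal communication, not systematic collection, but it lends no support to the upper rows of the table.

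**Conclusion.** The point holds as a gap in descriptive reporting. Collection is per injection, the specified TEAE tables are per patient, and the Cohort 2 and overall percentages therefore mix tracer risk with number of injections. Under equal per-injection risk and non-negative within-patient dependence, the Cohort 2 figure lies between 1 and just under 2 times p. At p = 2% the gap is at most about two percentage points; at p = 10% it is at most nine.

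Reading this as a doubled Cohort 2 rate is not justified: that is a ceiling, needing independent events and a second injection in every Cohort 2 patient. Nor would a by-injection table isolate a repeat-dose effect, because every planned second injection in Cohort 2 follows neoadjuvant therapy and the two are confounded. The primary analysis is untouched.

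**What to change.** In SAP 10.7.1:

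1. Keep the per-patient tables, including the overall column, as they are.
2. Add the TEAE overview and the SOC/PT tables by injection. First injection: all dosed patients, by cohort and overall. Second injection: Cohort 2 patients dosed at Visit 3. The denominator is the number who received that injection, which SAP 10.5 already produces.
3. Use first-injection incidence wherever the cohorts are set against each other. It should not replace the overall per-patient statement, since that would drop second-injection events from the headline.
4. State how an event is assigned to an injection when it falls outside both windows or has a partial start date. One option is the latest injection before onset, with an unassigned row where the known part of the date does not decide.

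The cost is SAP wording and a little programming; onset dates (Protocol 7.2.4) and injection dates are already collected. Second-injection cells will be sparse. If half of 60 patients were dosed twice (assumed), there would be 30 second injections, an expected 30 x 0.05 = 1.5 patients with an event at p = 5%, and a one-sided 95% upper bound of 1 - 0.05^(1/30) = 9.5% if none occurred.
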